Yoga for generalized anxiety disorder: A comparison between yoga, cognitive behavioral therapy, and stress education training

Objectives

The general purpose of the study is to determine whether yoga is an effective method for treating GAD, and its relative efficacy compared to a standard psychosocial intervention. Our primary objective is to examine the short-term treatment efficacy of yoga on GAD symptoms. Our secondary objective is to examine the long-term treatment efficacy of yoga on GAD symptoms. Our tertiary objective is to examine and compare the mechanism of treatment changes in yoga and traditional CBT for GAD.

Design and Outcomes

This five-year multi-site study will examine the comparative efficacy of yoga, CBT, and stress education, a previously employed control condition, for patients with GAD. Across 2 enrolling centers (BU and MGH) we will randomize 230 patients with GAD to one of three 12 session weekly study treatments: 12-weekly yoga (n=95), CBT (n=95), or stress education (SE: n=40). Independent clinical assessments will occur before the 12-session intervention phase, at mid-treatment, after the intervention, and at 6-month follow-up. All clinician-rated outcomes will be assessed by trained Independent Evaluators (IEs) blind to treatment assignment. Response (CGI-I of 1 or 2) will serve as the primary outcome measure alongside the SIGH A as the core secondary continuous measure. Secondary outcome measures also include the STAI, PSS, BDI-II and BAI, QOL, ISI, PSQI and PSWQ. The FFMQ, MCQ, pre-ejection period, and cortisol are examined as possible mediators of change. The Credibility/Expectancy Questionnaire will be administered to examine whether credibility and expectancy moderates therapy outcome. In addition, we will explore whether clinical characteristics (comorbid diagnoses) and demographic characteristics (age, sex, SES) are possible moderators. We hypothesize that Yoga and CBT will each be superior to SE at post-treatment FU, and Yoga and CBT will not differ based on equivalency analyses. We predict that treatment changes during yoga are mediated via changes in mindfulness and changes in vagal tone, whereas changes in CBT are mediated via changes in maladaptive cognitions.

Interventions and Duration

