9.5.1 Primary Outcome

Response (CGI-I of 1 or 2) will serve as the primary outcome measure alongside the SIGH-A as the core secondary continuous measure.

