This growth curve model will be used to test differences between treatment conditions for our primary outcome (response to treatment) and for CGI-S, since these outcomes are measured frequently enough (7 times during treatment) to accurately model the growth curve. However, the other secondary outcomes are measured at most3 times during treatment (baseline, week 6, post-treatment), with secondary sleep measures administered only twice (baseline and posttreatment), thus disallowing accurate assessment of their growth curve. Thus, these outcomes will use an MRM employing an ANOVA type design (see for example, Liu, Rovine, & Molenaar, 2012). In this kind of model, time is treated as a categorical variable (using2 dummy variables [one for each assessment except the baseline assessment] to code the 3 assessments). The three treatment conditions (Yoga, CBT, and SE) will be coded using the 2 dummy variable contrasts (Yoga vs. SE and CBT vs. SE). Interactions will be formed between each treatment condition contrast and each assessment dummy variable. This coding freely estimates the means for the outcome at each assessment, without any constraint from a specific growth curve. This design is similar to a 3 x 3 repeated measures ANOVA with the exception that it includes all patients that complete at least one assessment, the outcome can be dichotomous, the covariance structure of the repeated measures can take almost any form, and this approach assumes data are missing at random (MAR) or not missing completely at random (MCAR). The significance of the interaction between a treatment condition contrast (e.g., Yoga vs. SE) and an assessment dummy variable (e.g., for the post-treatment assessment) will test whether the change from baseline to that assessment is significantly different between the treatment conditions. Using this coding scheme, all contrasts between treatment conditions at all assessments are provided by this one analysis. Thus, this approach has the added benefit of having all contrasts between the treatment conditions at each assessment being conducted on the same sample.

Demographics and comorbid diagnoses will be used as covariates in all analyses and considered as possible moderators of outcome at each assessment. An additional moderator that will be investigated is homework adherence.

Planned Secondary Analysis of Sensitivity of Growth Curve Model for Primary Outcome

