To determine if the results of the analyses for Aim 1 are sensitive to the growth curve model, we will perform a secondary analysis, using a simple ANCOVA-type model, to verify the results of our primary growth curve model. Since the outcome is binary (response to treatment), this analysis will be performed using logistic regression, with the following predictors of outcome at post-treatment: baseline severity based on the CGI-S and SIGH-A, and the two dummy variables coding the contrast between SE and the 2 active treatments. This analysis will be performed twice: once as an ITT analysis with missing outcomes imputed as last observation carried forward, and once as a completer analysis.

Per Protocol Secondary Analysis:

As additional secondary analyses, we will repeat our GLMM and MRM analyses using the per protocol sample. We will use these analyses rather than simpler analyses (such as logistic regression or repeated measures ANOVA) because repeating our GLMM and MRMs will allow a more direct comparison to the results for the intent-to-treat sample, allows inclusion of subjects that miss some assessments (other than baseline and post-treatment), allows the modeling of complex covariances between the repeated measures, and it assumes MAR rather than MCAR.

Follow Up Secondary Analyses:

Analyses of outcome at FU (Aim 2) will be considered exploratory since subjects may seek additional treatment during follow-up. These analyses will follow the analyses of outcome at post-treatment, except one additional assessment (FU) will be added to these analyses. Since response during FU may not follow the growth curve of the treatment phase, the growth curve for Aim 2 will be modeled as "piecewise", separately modeling the growth curve during treatment and follow-up. (Analyses of the secondary outcomes at FU will follow the mixed effects ANOVA model described above since these analyses include only 4 total assessments). We will add an additional dummy variable predictor to the analyses for Aim 2, coding whether or not the subject received additional treatment during FU. We will also add the interactions of this "additional treatment" variable with all the other predictors in the analyses to determine if "additional treatment" impacted response to treatment at FU. This analysis will

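### The model for SIGH-A and the other continuous secondary outcomes except CGI-S leaves baseline means free by arm, giving up precision that a common-baseline model would recover at almost no cost

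*Combined protocol and SAP*

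**What the plan says.** Section 9.5.1 sets response as the primary outcome, "alongside the SIGH-A as the core secondary continuous measure". Section 9.6 gives response and CGI-S a growth-curve model. The remaining secondary outcomes, with two or three assessments up to post-treatment, get a mixed model with time as a categorical variable: two arm dummies (yoga vs SE, CBT vs SE), a dummy for each post-baseline visit, and all their interactions. Of this model the plan says:

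- On the means: "This coding freely estimates the means for the outcome at each assessment, without any constraint from a specific growth curve"
- On the layout, by analogy: "This design is similar to a 3 x 3 repeated measures ANOVA"
- On the test, the arm-by-visit interaction "will test whether the change from baseline to that assessment is significantly different between the treatment conditions"
- On the covariance: "the covariance structure of the repeated measures can take almost any form"

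On adjustment, "Demographics and comorbid diagnoses will be used as covariates in all analyses"; the outcome's own baseline score is not listed. Baseline adjustment appears only in the logistic sensitivity analysis of binary response, whose predictors include "baseline severity based on the CGI-S and SIGH-A". The Follow Up Secondary Analyses paragraph reuses the categorical-time model for the secondary outcomes.

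Section 4.3 randomizes participants after the baseline assessment, and releases the code only once the last member of a treatment group has completed baseline.

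**The concern.** In a three-arm, three-visit model with nine free cell means, baseline is an outcome with a separate mean in each arm. The interaction then subtracts the whole observed baseline difference between arms from the post-treatment difference. Because baseline precedes randomization, that difference is chance alone. The best correction subtracts only the part that predicts the post-treatment score, and a common baseline mean does this automatically.

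At stake is the width of the confidence intervals for SIGH-A, STAI, PSS, BDI-II, BAI, PSWQ, the sleep scales and the rest. It matters most in the two superiority contrasts, which are limited by the SE arm of 40.

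**Working it through.** **Inputs from the documents.** 95 yoga, 95 CBT and 40 SE (Précis); 25% missing data assumed for the continuous superiority tests (section 9.2); three-level model with treatment cohorts of 4–6 (section 9.6).

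**Inputs assumed.** Baseline-to-post correlation rho of .3 to .7, equal SDs at first, two-sided alpha .05. The documents give none of these.

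**The plan's own figure.** Section 9.2 reports more than .80 power at d = .27. This can be neither reproduced nor refuted, because the variances and covariances put into the power program are not given. A simple two-sample calculation gives a detectable difference of 2.80 × sqrt(1/95 + 1/40) = .53 SD, or .61 with 25% loss (71.25 vs 30). Reaching .27 that way would need rho of about .86 to .90.

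**Variance of the post-treatment contrast, equal SDs, complete data.** In units of the post-treatment variance:

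- free baseline (raw change): 2(1−rho)
- common baseline: 1−rho²
- ratio: (1+rho)/2, so the saving is (1−rho)/2

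The missing-data column comes from exact generalized least squares for the three-arm, three-visit model. It assumes 25% missing at post-treatment and 10% at week 6, under two correlation patterns. The last column is the yoga-vs-SE difference, in SD, detectable with .80 power at 95 vs 40 with complete data.

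| rho | free | common | saving | saving, 25% missing | detectable, free to common |
|---|---|---|---|---|---|
| .3 | 1.40 | .91 | 35% | 29–30% | .625 to .504 |
| .5 | 1.00 | .75 | 25% | 20–21% | .528 to .457 |
| .7 | .60 | .51 | 15% | 12% | .409 to .377 |
| .9 | .20 | .19 | 5% | not run | .236 to .230 |

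**Unequal SDs.** Let k be the baseline SD divided by the post SD. The free-baseline factor becomes k² + 1 − 2·rho·k, so the saving is (k−rho)² / (k² + 1 − 2·rho·k). At rho .3, .5 and .7:

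- k = .8: 22%, 11%, 2%
- k = .7: 15%, 5%, 0%

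The saving is never negative. It is zero when k equals rho, and exceeds the equal-SD value when k is above 1.

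**Clustering.** Cohort variance that arises during treatment is not removed by baseline adjustment. With an assumed intraclass correlation of .05 and groups of 5, both factors gain (5−1) × .05 = .20. The savings become 1 − 1.11/1.60 = 31%, 1 − .95/1.20 = 21% and 1 − .71/.80 = 11%.

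**A partial check on rho.** The 16-patient GAD yoga pilot in section 2.2 reports paired t(15) and d scaled by the baseline SD, so SD(change)/SD(baseline) = 4d/t:

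- anxiety: 4 × .86/4.88 = .70
- depression: 4 × .96/4.98 = .77
- global severity: 4 × .76/4.58 = .66

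With equal SDs, rho = 1 − (ratio²)/2, which is about .75, .70 and .78. The saving is then about 12%, 15% and 11%. The pilot does not report the post SD. If it shrank as in the adolescent-musician yoga group (17.8 to 15.4, a different population and scale), the saving would be 27–30%. If it grew by 10%, it would be 3–6%. One small uncontrolled group is indicative only.

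**The case against.** The strongest reply is that the planned test is valid, so this is a preference between accepted models. That stands as far as validity goes. A reader might infer bias from the remark that raw change over-corrects chance baseline imbalance, but over-correction is the same inefficiency in other words: on average over randomizations the contrast is unbiased.

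A second reply is that the gain could be very small. This also stands. Entry requires CGI-S of 4 or higher, which may compress baseline severity and push k below 1, and the arithmetic above shows how quickly the saving then shrinks. A reader might take 15–35% as established; the documents do not support that. It is a range under assumed rho, equal SDs, complete data and independent patients. Nor is it a share of all the variance reduction that randomization makes possible.

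A third reply is that the sentence on free means concerns the shape over time and does not expressly put arm effects at baseline. The comparison to a 3 × 3 ANOVA and the stated test of change from baseline make the free-baseline reading the natural one, and no common-baseline constraint is stated. The flexible covariance structure does not supply one either.

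**Conclusion.** The point holds as a loss of efficiency. For the continuous secondary outcomes other than CGI-S, the planned model ignores equality of baseline means that the design guarantees. With the covariance correctly modelled, a common-baseline model is never less precise in expectation. With equal SDs and complete data the contrast variance falls by 15–35% for rho .7 to .3, so confidence intervals narrow by about 8–19% (1 − sqrt(.85) to 1 − sqrt(.65)). With 25% missing the variance saving is about 12–30%. Clustering lowers it further, and it approaches 0 as the baseline SD nears rho times the post SD. The pilot points to 11–15% if SDs are equal.

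Two wider inferences are not supported. The binary primary outcome, the non-inferiority sample size and CGI-S do not rest on this model. And the d = .27 power statement is not shown to be wrong: its inputs are undisclosed, and if rho were near .9 the saving would be only about 5%.

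**What to change.** Keep the three-level mixed model, the visit dummies and the intent-to-treat sample. Drop the two arm main effects, which in this coding are the baseline differences, so that the three arms share one baseline mean. Specify a covariance structure that lets variances and correlations differ by visit. Test the arm-by-post-treatment terms. Use the same form for the two-visit sleep measures and for the arm contrasts at follow-up.

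Do not describe a model of post-baseline visits only, with baseline as a covariate, as equivalent. It excludes patients with only a baseline assessment, whom section 9.3 keeps in the intent-to-treat sample.

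Equality of baseline means is guaranteed only for the arms as randomized. The constraint should not carry over automatically to the per-protocol sample, or to comparisons within groups defined by additional treatment or dropout pattern.

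The cost is a short SAP amendment before unblinding and two fewer model terms. No new data are needed.

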Interested patients who are eligible for participation will be scheduled for an evaluation meeting where informed consent will be obtained. All potential participants will review the consent form, risks, and benefits associated with the protocol with an approved study investigator and will sign consent prior to completion of any study assessments in this protocol. The study investigator will explain the study, answer any questions, and obtain written informed consent. Participants will be given as much time as needed to review the consent and ask questions prior to participation in study procedures. The study procedures and consent form will be approved by the Institutional Review Board at each of the participating sites prior to study initiation.

Potential participants will undergo formal structured clinical interviews and rating scales (see Assessment section 6.2 for detail) to confirm diagnosis and eligibility. Patients will then undergo safety assessments including medical history, medication use, and laboratory tests, including urine toxicology screen and pregnancy test (for women of childbearing age). In addition, our MD or nurse with MD oversight familiar with the yoga intervention will determine whether the participant is fit for yoga and CBT based on a baseline medical history and physical exam to determine whether study exclusion criteria are met, and any identified medical concerns will be reviewed with signed permission with participant's PCP prior to study entry. We expect to screen and consent approximately 295 individuals such that 230 will meet eligibility criteria and agree to be randomized across the 2 sites.

Randomization Procedure

After eligibility criteria are determined and participants have completed a baseline assessment, and confirmed availability to participate, participants will be randomly assigned to either Yoga, CBT, or stress education (SE) using the variable-sized permuted block randomization procedure (stratified by site).

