Structured Diagnostic Interview (SCID): The Structured Clinical Interview for DSM-IV (SCID-IV: will be updated to SCID5 as soon as available, anticipated prior to enrollment) will be administered at MGH CATSD to determine the absence of diagnostic exclusion criteria and assess co-occurring psychiatric disorders. The Anxiety Disorders Interview Schedule for DSM-5 (ADIS-5; [92]) will be used at BU to determine DSM-5 psychiatric diagnoses (please note that the ADIS-5 was developed at the Center for Anxiety and Related Disorders at Boston University, therefore, this interview is already available to us).

Each principal investigator has extensive experience with diagnostic interviews, and all raters will be certified. Cross site certifications and quality assurance ratings will occur to assure rating consistency of diagnoses as administered in the SCID with the ADIS, an overlapping interview.

Clinical Global Impression of Severity (CGI-S; [94-97]): This is a 1-item scale asking the investigator to assess the patient's overall level of illness severity. The clinician should integrate all aspects of the patient's condition when using this scale. It will be used at assessments.

Clinical Global Impression of Improvement (CGI-I; [93]): This 1-item instrument allows evaluators to give an overall rating to subject's level of improvement or worsening on a scale of 1-7, with 1 correlating to very much improved and 7 correlating to very much worse. It will be used at assessments.

Structured Interview Guide for the Hamilton Anxiety Rating Scale (SIGH-A; [98]) This 19-item structured, clinician-administered rating scale provides an overall measure of anxiety. It will be used at assessments.

Self-Report Measures

Demographics Form: Patients will be asked to fill out a questionnaire regarding age, race, ethnicity, gender, socioeconomic status in addition to their religious beliefs and practices.

State-Trait Anxiety Inventory (STAI; [100]): The STAI-A is a 40-item, multiple-choice questionnaire that differentiates between the temporary condition of "state anxiety" and the more general and long-standing quality of "trait anxiety." As a result, it is useful in both clinical and research contexts. It will be used at assessments.

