6.2.3 Blinding

Independent evaluators will remain blind to treatment assignment throughout the study. To preserve the blind they will be instructed with a reminder script for patients not to discuss their treatment prior to an assessment. The randomization codes will be created by the study statistician prior to entry of the first patient in the trial. Randomization will be stratified only by site. No unblinded analyses will be performed prior to study completion, unless specifically requested by the DSMB, in which case study PIs will only see blinded safety comparisons of the study intervention groups.

The trainers/therapists and the person handling the randomization code cannot be blinded, but they will not be involved in IE ratings, which will be used for outcomes in this trial. The PIs will supervise the treatments, and oversee all study participants including safety and adverse events. The PIs will not, however, know the subject's patient codes and the PIs will not be involved in the independent evaluator ratings. Thus these clinical and oversight study staff will not have access to data and have no influence on the outcome data. Outcome ratings will be completed by the blinded independent evaluators. The data management and analysis will be completed by the study statisticians and data manager who are not involved in clinical treatment or safety assessment at any time.

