9.5.2 Secondary Outcomes

Secondary Outcomes: Secondary outcome measures include the STAI, PSS, BDI-II and BAI, WHOQOL-BREF, PSQI, ISI, ASQ, and PSWQ. The FFMQ, MCQ, RSA, and cortisol are examined as possible mediators of change.

The Credibility/Expectancy Questionnaire will be administered to examine whether credibility and expectancy moderates therapy outcome.

In addition, we will explore whether clinical characteristics (comorbid diagnoses) and demographic characteristics (age, sex, SES) are possible moderators. The data analyses are described for the primary measure only.

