9.6 Data Analyses

Primary Analyses

Our primary analyses will use mixed-effects regression models (MRMs) with a logistic linking function (a GLMM analysis) since our primary outcome measure (response to treatment, defined as CGI-I≤2) is dichotomous. Analyses of secondary outcomes will be performed using MRM. MRM and GLMM easily accommodate nesting of repeated observations within subjects, include all subjects with at least one assessment, and are the preferred method to analyze longitudinal data (Hamer and Simpson, 2009 [135]). Since these analyses will include all subjects who are randomized and complete at least one assessment, it is an intent-to-treat analysis. Also, since subjects will undergo treatment in groups (4-6 subjects per group) our MRM and GLMM models will include 3 levels: repeated measurements (level 1) nested within subjects (level 2) who will be nested within their treatment cohort (level 3).

Our primary model will be a GLMM in which response to treatment over time will be modeled as a growth curve. Our primary analyses will examine outcomes at post-treatment (Aim 1). These analyses will include only the 7 assessments from baseline to post-treatment, and will not include the follow-up (FU) assessment since it could be affected by subjects seeking other treatments during the FU period. Only our exploratory analyses for outcome at FU (Aim 2) will include data from the FU assessment. Since recent research indicates that suboptimal modeling of the growth curve can result in incorrect results, we will examine various linear and nonlinear models to find the optimal growth curve during treatment (linear, quadratic, cubic, exponential [leveling off at an asymptote], and an ANOVA model, in which time is coded as a categorical variable. For this ANOVA model, each assessment time point is modeled with a dummy coded assessment variable [coded 1 for the assessment, 0 for other assessments]. In this model, the means at each assessment point are freely estimated and are not constrained to fit any particular pattern. See our discussion of the ANOVA model in the paragraph below for more information).We will conduct our significance tests using the growth curve that most accurately models the data (comparing the various growth curve models using AIC and BIC).

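### The primary response model names neither site nor baseline severity, while an unlisted set of demographics and comorbid diagnoses is assigned to all analyses

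*Combined protocol and SAP*

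**What the plan says.** Section 9.6 defines the primary analysis: "Our primary model will be a GLMM in which response to treatment over time will be modeled as a growth curve". The description gives time centred at week 12, two treatment contrasts against stress education (SE), and three levels: measurement, subject and treatment cohort. It names no site term and no baseline severity term.

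Covariates come in one later sentence of the same section: "Demographics and comorbid diagnoses will be used as covariates in all analyses". The sentence goes on to treat the same variables as candidate moderators. The set is not listed. Section 9.5.2 gives a narrower list, but for moderators: "we will explore whether clinical characteristics (comorbid diagnoses) and demographic characteristics (age, sex, SES) are possible moderators". The demographics form in section 6.2 collects more: "age, race, ethnicity, gender, socioeconomic status in addition to their religious beliefs and practices". Comorbid diagnoses are not enumerated anywhere.

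On the design side, section 6.2.3 says "Randomization will be stratified only by site", and sections 4.3 and 9.2 agree. A footnote to the schedule in section 6.1 says that CGI-I is not rated at screening or baseline.

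The secondary logistic model for Aim 1, also in section 9.6, has "baseline severity based on the CGI-S and SIGH-A" and the two treatment dummies as its predictors. Site, demographics and comorbid diagnoses are not among them.

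**The concern.** There are three problems.

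- **Site.** An analysis should normally reflect the factor used to stratify randomization. Here it is not in the described model.
- **Severity.** Baseline severity is the obvious prognostic candidate, and the plan itself selects it for the secondary model. The primary outcome has no baseline measurement, so nothing in the primary model stands in for it.
- **Conflict within section 9.6.** If demographics enter all analyses, the predictor list of the logistic model is incomplete. If that list is complete, the statement about all analyses is wrong. On the second reading, a difference between the growth-curve result and the logistic result cannot be put down to the growth curve, which is what that model is meant to check.

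At stake are some power, a clean sensitivity analysis, and a covariate set that is fixed before outcomes are compared by arm.

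**Working it through.** **Inputs.** Allocation is 95 yoga, 95 CBT and 40 SE (Précis). Planning response rates are 57.9% for CBT and 22.2% for placebo (section 9.2). I take yoga as equal to CBT and SE as equal to placebo. The documents give no covariate count and no prognostic strengths, so these are assumed over a range.

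**The plan's own figure.** Margin: (57.9 − 22.2)/2 = 17.85 points. With one-sided alpha .05 (not stated, but implied) and power .80, n per arm = (1.645 + 0.842)² × 2 × .579 × .421 / .1785² = 94.6, or 95. This reproduces the plan's 95 per arm. The calculation contains no covariates.

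**Events available.** Responders: 2 × 95 × .579 + 40 × .222 = 110.0 + 8.9 = 118.9. Non-responders: 230 − 118.9 = 111.1. All arms share one model, so the limit for covariate main effects is the rarer outcome, 111.1. Events per parameter = 111.1/(k + 2), where k is the number of covariate terms and 2 counts the treatment contrasts.

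**Overfitting.** The simulation used a single-time-point logistic model at week 12, covariates with no true effect, and 4,000 runs per setting. The true log odds ratio, yoga versus SE, is ln(.579/.421) − ln(.222/.778) = 1.573.

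| k | Events per parameter | Median log OR (excess over 1.573) | Type I error, all rates 22.2% | Type I error, all rates 50% | Power |
|---|---|---|---|---|---|
| 0 | 55.6 | 1.593 (1%) | 4.4% | 4.6% | .979 |
| 5 | 15.9 | 1.618 (3%) | 4.6% | not run | .978 |
| 10 | 9.3 | 1.673 (6%) | 5.5% | 6.1% | .978 |
| 20 | 5.1 | 1.762 (12%) | 5.6% | 6.2% | .974 |
| 25 | 4.1 | 1.797 (14%) | 5.4% | not run | .970 |

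The simulation error on a type I rate near 5% is √(.05 × .95/4000) = 0.3 points. A similar simulation with 4 to 8 terms and 5,000 runs gave 4.1 to 5.2%.

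**Baseline severity.** Response rates were 45% versus 22.2%, a smaller contrast than planned, because power at the planning rates is already near .98.

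- Log odds ratio 0.5 per SD: power .726 unadjusted, .734 adjusted (gain 0.8 points).
- Log odds ratio 1.0 per SD: power .734 unadjusted, .784 adjusted (gain 5.0 points).

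The simulation error of each power figure is about √(.73 × .27/4000) = 0.7 points, so the first gain cannot be told from zero.

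**Site.** With an assumed site log odds ratio of 0.5 or 1.0, type I error without a site term was 5.0% and 4.8%. With the term it was 4.6% and 4.9%. The effect of site on power was not computed.

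**Moderators.** Here the 8.9 expected SE responders do bind, because each treatment-by-covariate term needs them. In 2,000 runs per setting, separation or non-convergence occurred in 17% of runs with 3 moderators, 28% with 5, 49% with 8 and 59% with 10.

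**Limit.** These are week-12 models with no random effects. The planned three-level model adds time terms and variance components, but also repeated observations, and neither is represented here.

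**The case against.** A reader might infer from the covariate sentence that the primary model is overfitted, with 20 or more terms resting on about 9 SE responders. The documents do not support that. The text says demographics, not all demographics. The only list spelled out for analysis, in section 9.5.2, is age, sex and SES, there as moderators. Race, ethnicity and religion come from a data-collection form, and nothing says that each comorbid diagnosis gets its own term. Shared main effects draw on about 111 non-responders, not on 9 responders in one arm. With 4 to 8 terms the harm is close to nil.

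A reader might also infer that the rule adds weak covariates and drops the useful ones. The prognostic value of neither set is given. Entry requires CGI-S of 4 or higher, which narrows the severity range, and CGI-I already rates change from baseline. Both could make severity a weaker predictor than assumed. Severity is also not absent from the plan, since the secondary logistic model adjusts for it.

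On site, section 4.3 forms groups of 4 to 6 within site strata, and cohort is a random level, so cohort can absorb part of a site difference. Omitting site did not inflate type I error.

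All of this limits the size of the point. It does not remove it. Cohort is not a site term, the covariate list remains open, and the two parts of section 9.6 still disagree.

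**Conclusion.** The point holds as one of specification, with a modest gain. As written, the primary response model names neither the stratification factor nor baseline severity, and the covariate rule conflicts with the predictor list of the model meant to check it.

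For severity, the power gain runs from nothing measurable to about 5 points, on assumed strengths of 0.5 to 1.0 per SD and a 45% versus 22.2% contrast. The reason to include site is that analysis should follow design. No numerical gain is claimed for it, and a reading that its omission biases the test or inflates type I error is not supported.

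Overfitting would matter only if about 20 or more covariate terms entered. At 10 it amounts to roughly 6% on the log odds ratio and a type I error of 5.5 to 6.1%. The plan leaves either count possible, which is the reason to fix the list. Aligning the covariates will not make the logistic check a pure test of the growth curve, because it also handles missing data differently, but it removes one avoidable difference.

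**What to change.** Change section 9.6 as follows:

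- **Primary response model:** add site, baseline CGI-S and baseline SIGH-A as fixed covariates.
- **Secondary logistic model:** keep baseline CGI-S and SIGH-A, and add site.
- **Secondary mixed models:** add site. Do not add an outcome's own baseline as a covariate where baseline is already one of the repeated outcome values (CGI-S, SIGH-A and the other mixed models). The treatment-by-assessment terms already test change from baseline, and the value would stand on both sides of the model.
- **Demographics and comorbidity:** replace the open phrase with a short fixed list with stated coding, for example age, sex, SES and any comorbid diagnosis (yes/no). Use the same list in the primary and the logistic model.
- **Moderators:** label treatment-by-covariate terms exploratory and keep them out of the primary model.

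Size check: site, CGI-S, SIGH-A, age, sex and comorbidity make 6 terms. With SES coded in 1 to 3 terms (assumed), k is 7 to 9, so events per parameter are 111.1/9 = 12.3 to 111.1/11 = 10.1.

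The cost is SAP wording, settled before any comparison by arm. All the variables are already collected, and there is no change to sample size, visits or conduct. This is a free improvement.
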